7.1.1. Dose Adjustment/Stopping Pharmacokinetic Criteria

The following dose adjustment / PK stopping criteria will apply:

- Dose escalation will be stopped if any single participant reaches exposures greater than PK stopping criteria threshold exposures ($AUC(0-\infty)$] of 48700 ng×h/mL and C_{max} of 6100 ng/mL in the SAD part of the study; AUC_{24h} of 48700 ng×h/mL and C_{max} of 6100 ng/mL for the MAD part of the study at steady state). (see

Section 4.5.3). We intend to use the PK dose escalation rule for progression to the next dose or dose adjustment which will involve establishing a relationship between exposures (AUC & C_{max}) vs dose using a power model and linear mixed effect modeling once PK data are available from a minimum of two prior dose levels. This model will be continually updated with incorporation of new dose levels as they become available. This developed model will be used to project exposure for the next dose level.

- If 95th percentile of predicted exposure from the maximum total daily dose is predicted to reach the PK stopping criteria exposure, dose escalation will be stopped, or dose adjustment will be planned, as appropriate. The Dose Escalation Committee will decide based on emerging safety, tolerability and PK information whether to evaluate any lower doses or repeat doses already evaluated in remaining periods to collect additional safety and PK data.

7.1.2. Dose Escalation / Study Stopping Criteria

The Principal Investigator and the GSK Medical Monitor will review the following and study dosing **will be** stopped if any of these criteria are met:

- Two or more participants from the previous dose level on active treatment experience an AE which is of severe intensity and reasonably attributable (in the opinion of the investigator) to dosing with GSK3494245.
- One or more participants across all study parts develop an adverse renal event as defined in the renal withdrawal criteria below (Section 7.1.3) considered to be related to GSK3494245 (in the opinion of the investigator in consultation with the Medical Monitor).
- One or more participants from any dose level experiences a serious adverse event which has a reasonable possibility of relation to investigational product.
- The dose escalation/study progression will be temporarily halted, and no further dosing will occur until a full safety review of the study has taken place. Relevant reporting and discussion with the GSK medical monitor, relevant GSK personnel, regulatory authorities and the Independent Ethics Committee will then take place prior to any resumption of dosing.

All other stopping criteria will apply even if no PK stopping criteria have been met.

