4.1.4. Multiple Ascending Dose (MAD)

Prior to initiation of the MAD part, a review of all available safety, tolerability and PK data from the SAD part will be conducted. A formal interim analysis is not planned.

[figure not shown]
MAD consists of 5 cohorts (Cohorts 4, 5, 6, 7 and 8), each including 8 participants. Participants in each cohort will be randomised to receive repeat doses in the fed state of either GSK3494245 or placebo (blinded), administered in a 3:1 ratio according to the randomization schedule.

GSK3494245 or placebo will be administered BID for 7 days using a 12 h dosing interval, with only one dose administered on Day 7. Based on emerging data, the dosing regimen

may be altered to a three-times daily (TID) regimen, with doses administered 6 hours apart on each day

Up to a maximum of 5 dose levels will be studied in the MAD part as illustrated below:

Figure 2 Study Design (MAD part)

A = active drug; BID = twice-daily; TID = three-times daily; DL = dose level; P = placebo. Day 7 is morning dose only.

Note: For each new dose level the first two subjects in each cohort will act as sentinels.

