7.1.8. Individual Safety Stopping / Withdrawal Criteria

- If a participant experiences a serious or severe clinically significant AE that in the clinical judgement of the Investigator is possibly, probably or definitely related to investigational product. It is **recommended** that the medical monitor is consulted before a decision is made.
- The participant initiates treatment with any prohibited medications.
- If any of renal, liver chemistry, ECG and telemetry, olfactory or mitochondrial toxicity stopping criteria are met (see Section 7.1.3, Section 7.1.4, Section 7.1.5, Section 7.1.6 and Section 7.1.7).
- The participant develops stomach erosion as confirmed clinically and following a gastro enterology specialist's opinion for further management, and endoscopy (if required).
- If a participant develops COVID-19 like symptoms during the study the following actions should be taken:
 - Participants who develop a high clinical index of suspicion for COVID-19 disease should be isolated and tested for COVID-19 in accordance with site procedures.
 - Assessments should be continued as per the protocol during this period; withdrawal of participants from the study will be at the discretion of the Principal Investigator but should first be discussed and agreed with the Medical Monitor.

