7.1.9. Group Safety Stopping Criteria

In addition to the criteria specified above, AEs, SAEs, laboratory abnormalities, ECG abnormalities and changes in vital signs occurring across all randomized participants will be regularly reviewed by the DEC in order to ensure appropriate participant safety. Any changes to the study due to safety reasons will be promptly communicated to the appropriate Regulatory Authorities and Independent Research Ethics Committee.

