10.3.2. Definition of SAE

If an event is not an AE per definition above, then it cannot be an SAE even if serious conditions are met (e.g., hospitalization for signs/symptoms of the disease under study, death due to progression of disease).

An SAE is defined as any untoward medical occurrence that, at any dose, meets one or more of the criteria listed:

a) Results in death

b) Is life-threatening
 
The term 'life-threatening' in the definition of 'serious' refers to an event in which the participant was at risk of death at the time of the event. It does not refer to an event, which hypothetically might have caused death, if it were more severe.

c) Requires inpatient hospitalization or prolongation of existing hospitalization
 
In general, hospitalization signifies that the participant has been detained (usually involving at least an overnight stay) at the hospital or emergency ward for observation and/or treatment that would not have been appropriate in the physician's office or outpatient setting. Complications that occur during hospitalization are AE. If a complication prolongs hospitalization or fulfills any other serious criteria, the event is serious. When in doubt as to whether "hospitalization" occurred or was necessary, the AE should be considered serious.
 
Hospitalization for elective treatment of a pre-existing condition that did not worsen from baseline is not considered an AE.

d) Results in persistent disability/incapacity
 
 • The term disability means a substantial disruption of a person's ability to conduct normal life functions. • This definition is not intended to include experiences of relatively minor medical significance such as uncomplicated headache, nausea, vomiting, diarrhea,

An SAE is defined as any untoward medical occurrence that, at any dose, meets one or more of the criteria listed:
influenza, and accidental trauma (eg, sprained ankle) which may interfere with or prevent everyday life functions but do not constitute a substantial disruption.
e) Is a congenital anomaly/birth defect
f) Is a suspected transmission of any infectious agent via an authorised medicinal product

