10.3.3. Recording and Follow-Up of AE and SAE

AE and SAE Recording

 • When an AE/SAE occurs, it is the responsibility of the investigator to review all documentation (eg, hospital progress notes, laboratory, and diagnostics reports) related to the event. • The investigator will then record all relevant AE/SAE information. • It is not acceptable for the investigator to send photocopies of the participant's medical records to GSK in lieu of completion of the GSK required form. • There may be instances when copies of medical records for certain cases are requested by GSK. In this case, all participant identifiers, with the exception of the participant number, will be redacted on the copies of the medical records before submission to GSK. • The investigator will attempt to establish a diagnosis of the event based on signs, symptoms, and/or other clinical information. Whenever possible, the diagnosis (not the individual signs/symptoms) will be documented as the AE/SAE.

Assessment of Intensity

The investigator will make an assessment of intensity for each AE and SAE reported during the study and assign it to one of the following categories:

- Mild: Asymptomatic or mild symptoms; clinical or diagnostic observations only; intervention not indicated.
- Moderate: Minimal, local or noninvasive intervention indicated; limiting age-appropriate instrumental Activities of Daily Living (ADL). Instrumental ADL refers to preparing meals, shopping for groceries or clothes, using the telephone, managing money, etc.
- Severe: Severe or medically significant but not immediately life-threatening; hospitalization or prolongation of hospitalization indicated; disabling, limiting self care ADL. Self care ADL refers to bathing, dressing and undressing, feeding self, using the toilet, taking medications, and not bedridden.

Assessment of Causality

- The investigator is obligated to assess the relationship between study treatment and each occurrence of each AE/SAE. The investigator will use clinical judgment to determine the relationship.
- A "reasonable possibility" of a relationship conveys that there are facts, evidence, and/or arguments to suggest a causal relationship, rather than a relationship cannot be ruled out.
- Alternative causes, such as underlying disease(s), concomitant therapy, and other risk factors, as well as the temporal relationship of the event to study treatment administration will be considered and investigated.

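### The severe-AE group stopping rule in Protocol 7.1.2 is limited to the previous dose level, so it does not clearly cover a MAD cohort still being dosed

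*Protocol*

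**What the plan says.** Protocol Section 7.1.2 gives three triggers that oblige the Principal Investigator and the Medical Monitor to stop dosing until a full safety review has been held. Each has its own scope:

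- Severe AEs: "Two or more participants from the previous dose level on active treatment experience an AE which is of severe intensity", with attribution to the drug in the investigator's opinion.
- Renal events: "One or more participants across all study parts develop an adverse renal event", as defined in 7.1.3 and considered related.
- SAEs: "One or more participants from any dose level experiences a serious adverse event which has a reasonable possibility of relation to investigational product".

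Two neighbouring sections also bear on severe AEs. Section 7.1.8 withdraws an individual: "If a participant experiences a serious or severe clinically significant AE that in the clinical judgement of the Investigator" is possibly, probably or definitely related. Section 7.1.9 says that AEs and other safety findings across all randomized participants "will be regularly reviewed by the DEC in order to ensure appropriate participant safety". It gives no count and no required action.

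Each MAD cohort has 8 participants, 6 of them active (Protocol 4.1.4; SAP 1.2). They are dosed BID, or TID if the regimen is changed, for 7 days, "with only one dose administered on Day 7".

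**The concern.** Of the three mandatory triggers, only the severe-AE one is tied to a dose level other than the one in use. In the SAD part this matters little, because each participant takes one dose per period. A MAD level is a week of repeat dosing. Two healthy volunteers could have related severe AEs partway through while the rest of the cohort still has many doses to take. Read literally, the trigger does not count those two cases, because their level is the current one. At the highest MAD level no later level follows, so on that reading the level never becomes the previous one.

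A mandatory rule exists so that the decision does not depend on judgement under pressure. Here its scope is unclear in a situation where it would be wanted.

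**Working it through.** The plan states no operating characteristic for this rule, so there is no figure to reproduce. The check is a comparison of the text, followed by a dose count for scale.

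**1. What previous means elsewhere in the protocol.** Section 4.6.2 (SAD) calls the level just dosed the current level and separates it from preceding levels. Section 4.6.3 (MAD) speaks of the previous repeat dose cohort when choosing the next level, a decision made once at least 4 active participants have completed 7 days. Neither use clearly takes in a cohort on, say, Day 3.

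**2. Whether another provision makes a group stop mandatory.**

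| Provision | Effect after two related, severe, non-serious, non-renal AEs |
|---|---|
| 7.1.2, SAE and renal triggers | Not met |
| 7.1.3, two-participant MAD halt | Renal markers only |
| 7.1.7 | Potential mitochondrial toxicity only; decided at escalation meetings |
| 7.1.8 | Withdraws the two affected participants only |
| 7.1.9 | DEC review, no threshold |
| 4.6 | Dosing may be halted (discretionary) |
| 4.6.3 | Halts escalation; does not say that dosing of the current cohort stops |

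None does.

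**3. Whether the remaining class of events is empty.** Severe intensity in 10.3.3 covers "hospitalization or prolongation of hospitalization indicated; disabling, limiting self care ADL". That overlaps with the SAE criteria but is not identical to them. The SAE disability criterion in 10.3.2 carries the note: "This definition is not intended to include experiences of relatively minor medical significance such as uncomplicated headache, nausea, vomiting, diarrhea". A gastrointestinal event that limits self care could therefore be graded severe without being serious on that criterion. The class is narrow but not empty.

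**4. Doses still scheduled.**

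Inputs: 6 active per cohort (8 × 3/4); one active sentinel; the other 5 active participants start at least 48 h later (4.1.5); a single dose on Day 7 (schedule of activities 1.3.2; SAP 1.2).

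- Doses per participant: BID 6 × 2 + 1 = 13; TID 6 × 3 + 1 = 19.
- Left after the end of Day d (d up to 6): BID (6 − d) × 2 + 1; TID (6 − d) × 3 + 1. After Day 7: 0.
- Both cases are assumed to be non-sentinels and to be withdrawn under 7.1.8. That leaves 3 non-sentinels, dosed together, and 1 sentinel two days ahead. Days below are those of the non-sentinel group.

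| Second case by end of | BID | TID |
|---|---|---|
| Day 2 | 3 × 9 + 5 = 32 | 3 × 13 + 7 = 46 |
| Day 3 | 3 × 7 + 3 = 24 | 3 × 10 + 4 = 34 |
| Day 5 | 3 × 3 + 0 = 9 | 3 × 4 + 0 = 12 |

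These are active doses that this trigger, read literally, would not block.

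**The case against.** The strongest reply is that previous is written from the viewpoint of the escalation decision. The heading of 7.1.2 names dose escalation, and 4.6.2 and 4.6.3 refer to it for that decision. Seen from there, the previous level is the one just dosed. Under 4.6.3 the meeting may be held once 4 active participants have finished, so up to 2 active members of the previous cohort could still be taking doses. The literal reading would also leave the first level uncovered while it is being dosed, which is an unlikely intention. This stands as a plausible account of what was meant. It does not settle the matter: 7.1.2 also governs study dosing, it sets no time of review, and a cohort in mid-course is not clearly covered on either reading.

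The second reply is that other safeguards apply. The affected participants are withdrawn, 4.6 allows a halt for any safety concern, and Section 8 requires immediate safety concerns to be discussed with the sponsor at once. This also stands, and the dose counts describe what is scheduled, not what would happen. But these group-level safeguards are discretionary, whereas 7.1.2 is meant to be mandatory.

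Third, Section 4.6.1 places stopping criteria in a DEC plan that is not among the documents. It may already set a current-level threshold.

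A reader might also infer that the restriction is an oversight from when the MAD part was added in Amendment 05. The documents do not show this. The amendment log is partly redacted, and Amendment 02 rewrote this same bullet and kept the phrase.

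**Conclusion.** The concern holds as an unclear scope in a mandatory safety rule. As worded, 7.1.2 does not clearly require a stop for two related, severe, non-serious, non-renal AEs in a MAD cohort still being dosed, the highest level included. On the Day 3 example, four other active participants would have 24 (BID) or 34 (TID) doses still scheduled. That count rests on the minimum 48 h stagger, on both cases being non-sentinels who are withdrawn, and on the other non-sentinels being dosed together.

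Two stronger readings are not supported. One is that the cohort would be unprotected: a single related SAE or renal event stops dosing, affected individuals are withdrawn, and dosing may be halted at discretion. The other is that the scenario is likely: the documents give no rate for related severe AEs and no share of them that would also be serious, so any probability would rest on assumption alone. The point is a worthwhile, cheap improvement, not a flaw that undermines the study.

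**What to change.** In the first bullet of 7.1.2, replace the limit to the previous dose level with: *at the current or previous dose level, including while dosing of a cohort is ongoing*. The Principal Investigator and Medical Monitor already named in that section would apply it. Use the same wording in the DEC plan.

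The change needs no new data, visits or staff. It costs the usual amendment approval and possibly an earlier pause in dosing. If the sponsor already means the level just dosed, the change only puts that in writing.

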7.1.3. Renal Stopping Criteria

For SAD and MAD - A participant that meets any of the following bulleted criteria will be withdrawn from the study:

- New onset of any clinically significant and persistent (within 48 hrs) haematuria as confirmed by microscopy.
- New onset of clinically significant and persistent (within 48 hrs) proteinuria (Spot Urine Albumin Creatinine (ACR) ratio $\geq 30\text{mg}/\text{mmol}$) in the absence of another clinical explanation e.g. calculus / infection.

- If there is any change in serum creatinine $> 26 \mu\text{mol/L}$ (0.3 mg/dl) from baseline or $> 50 \%$ from baseline. If change in serum creatinine measures at $> 26 \mu\text{mol/L}$ (0.3 mg/dl), repeat within 24 hrs. If confirmed, the participant will be withdrawn, and further investigations will be performed.

For MAD only - If two or more participants have a fall in $\text{eGFR} \geq 30\%$ or rise in $\text{SrCr} \geq 30\%$ accompanied by abnormality in any other renal markers, the study will be temporarily halted for evaluation.

[figure not shown]
7.1.4. Liver Chemistry Stopping Criteria

Hepatic Safety Panel Liver chemistry stopping and increased monitoring criteria have been designed to assure participant safety and evaluate liver event etiology.

Discontinuation of study treatment for abnormal liver tests is required when:

- a participant meets one of the conditions outlined in the algorithm or
- when in the presence of abnormal liver chemistries not meeting protocol-specified stopping rules, if the investigator believes study treatment discontinuation is in the best interest of the participant.

Phase I Liver Chemistry Stopping Criteria – Liver Stopping Event Algorithm

Abbreviations: ALT = alanine transaminase; INR = international normalized ratio; SAE = serious adverse event; ULN = upper limit of normal.

Refer to [Appendix 5](#) for required Liver Safety Actions and Follow up Assessments.

7.1.4.1. Study Treatment Restart or Rechallenge after Liver Stopping Criteria Met

Study treatment restart or rechallenge after liver chemistry stopping criteria are met by any participant in this study is not allowed.

7.1.5. ECG and Telemetry Stopping Criteria

A participant that meets either bulleted criterion based on the average of triplicate ECG readings will be withdrawn from study treatment.

QTc > 500 msec,

Change from baseline: QTc > 60 msec

- The *same* QT correction formula *must* be used for *each individual participant* to determine eligibility for and discontinuation from the study. This formula may not be changed or substituted once the participant has been enrolled. For example, if a participant is eligible for the protocol based on QTcB, then QTcB must be used for discontinuation of this individual participant as well.
- Once the QT correction formula has been chosen for a participant's eligibility, the *same formula* must continue to be used for that participant *for all QTc data being collected for data analysis*. Safety ECGs and other non-protocol specified ECGs are an exception.
- The average of triplicate ECG readings obtained over a brief (e.g., 5-10 minute) recording period.
- Withdrawal of participants is to be based on an average QTc value of triplicate ECGs. If an ECG demonstrates a prolonged QT interval, then obtain 2 more ECGs over a brief period of time and then use the mean QTc values of the 3 ECGs to determine whether the participant should be discontinued from the study.

OR

- Non-Sustained Ventricular Tachycardia (NSVT) > 3 beats or PVC triplets on telemetry.

7.1.6. Olfactory Stopping Criteria

- New onset changes in smell which cannot be explained by other causes following further investigations carried out as per Investigator's discretion, in consultation with the Medical Monitor.

7.1.7. Mitochondrial Toxicity Stopping Criteria

- Unexplained lactic acidosis as determined by the Investigator, in consultation with the Medical Monitor.
- Clinical symptoms, signs and clinical chemistry and haematology parameters will be reviewed by the Investigator, Safety and Medical Governance (SMG) lead and Medical Monitor during dose escalation meetings. A decision to withdraw individual

participants or stop the study based on potential mitochondrial toxicity would be made following this review.

- If a participant develops acidosis (where low pH is confirmed by the investigator) during the study, the following actions should be considered. Measurement of serum and urine ketones, chloride and calcium to be performed **contemporaneously** with low pH.
- If an acidosis adverse event is observed on a venous blood gas, an arterial blood gas test **may be performed** if deemed appropriate by the Investigator to inform the clinical care of the participant.

7.1.8. Individual Safety Stopping / Withdrawal Criteria

- If a participant experiences a serious or severe clinically significant AE that in the clinical judgement of the Investigator is possibly, probably or definitely related to investigational product. It is **recommended** that the medical monitor is consulted before a decision is made.
- The participant initiates treatment with any prohibited medications.
- If any of renal, liver chemistry, ECG and telemetry, olfactory or mitochondrial toxicity stopping criteria are met (see Section 7.1.3, Section 7.1.4, Section 7.1.5, Section 7.1.6 and Section 7.1.7).
- The participant develops stomach erosion as confirmed clinically and following a gastro enterology specialist's opinion for further management, and endoscopy (if required).
- If a participant develops COVID-19 like symptoms during the study the following actions should be taken:
 - Participants who develop a high clinical index of suspicion for COVID-19 disease should be isolated and tested for COVID-19 in accordance with site procedures.
 - Assessments should be continued as per the protocol during this period; withdrawal of participants from the study will be at the discretion of the Principal Investigator but should first be discussed and agreed with the Medical Monitor.

